Risks of this project to the subjects are judged to be small, the discomfort of having an MRI and a PET-scan, and the potential ear pressure during the HBOT sessions. Potential benefits include improved symptoms of cognitive function or slower rate of progression of dementia symptoms. Improved symptoms would be expected to improve patient quality of life. These potential benefits exceed the potential harm by HBOT to study participants. Additional possible direct benefits are those that might arise from a comprehensive cognitive and neuroimaging examination. Such assessments may provide clinically relevant information and lead to referrals for otherwise unrecognized cognitive or brain abnormalities that may require treatment. For this reason, the relatively small risks to subjects are reasonable in relation to the anticipated benefits to subjects and others.

4. Importance of the Knowledge to be Gained.

The overriding aim of this project is to examine the potential beneficial effect of HBOT on cognitive function in diabetic elderly who are at high risk of developing dementia since they already have mild cognitive impairment. The study will also examine whether HBOT affects beneficially the brain through improved cerebral blood flow and glucose uptake. Cognitive decline and dementia are major public health concerns today and will only become even greater concern in the future as longevity increases and the age structure of the population shifts toward increasingly older ages. Currently, approved treatment for dementia is only modestly effective, and it would be an important advance if HBOT will show effectiveness. In relation to this potential benefit, potential risks are reasonable.

5. Data Safety and Monitoring Board

A Data and Safety Monitoring Board (DSMB) will consist of four members, with expertise in the four areas relevant to this RCT: type 2 diabetes, cognitive aging, HBOT, and neuroimaging. No investigator involved in the trial is a member of the DSMB. The initial task of the DSMB will be to review the protocol, procedures and consent form to identify any necessary modifications. If modifications are necessary, revisions will be reviewed by the DSMB prior to its recommendation on initiation of the project. The modifications will be submitted and approved by the IRBs before study initiation. Throughout the study, any changes to the protocol will be submitted to the DSMB. The DSMB will identify the data parameters and format of the information to be regularly reported. The DSMB will be informed of the occurrence of any serious adverse events and immediately notified of fatal or life-threatening events. The DSMB may at any time request additional information from the PI. The DSMB will initially be provided with data blinded to treatment status, but they may request an unblinding if there is a safety concern. Based on the review of safety data, the DSMB will make recommendations regarding the conduct of the study. These may include amending safety-monitoring procedures, modifying the protocol or consent, terminating the study or continuing the study as designed. The discussions and decisions of the DSMB will be summarized in written reports and provided to the PIs. All DSMB reports will be shared with the Mount Sinai IRB, which is the supervisory IRB for this study and which will transfer these reports to the other 2 IRBs involved (Asaf Harfeh, Sheba) and will become part of the study regulatory binder. The DSMB will meet in person or by conference call on a quarterly basis. The DSMB will also provide advice regarding any discrepancies found by the data auditing system or other sources.

6. Data and Safety Monitoring Plan.

a. Data Quality The quality of the data will be monitored by the PIs. The following elements will be monitored: recruitment proceeding as expected; subjects fully match the inclusion/exclusion criteria; deviations

from the protocol; timeliness, accuracy, and confidentiality of all information both in study documents and database.

We are cognizant that overseeing a project that takes place in a geographically distant place and in another country poses challenges with respect to data quality and protocol adherence. The successful implementation of the IDCD study clearly demonstrates the feasibility of this international collaboration. In addition, we will conduct bi-weekly conference calls, one with the data collection team, and one with the senior investigators. Prior to each meeting, [name] sends an email compiling the issues that should be discussed. The investigators of the study have maintained, literally, email and phone contact on a daily basis. Drs. [name] and [name] work closely for over a decade. [name] has international collaborations with all other study investigators involving other projects in Israel (IDCD study, IRAP study) and travels every other month to Israel, for face to face meetings and review of data and procedures on site. The PIs of the Asaf Harofeh ([name]) and Sheba ([name]) sites are both physician scientists. Thus, the investigators have all the necessary expertise relevant for this RCT, have continuous contact, and are well integrated around this (and other) joint dementia-related projects.

b. Safety Monitoring Safety monitoring for adverse events (AEs) will be conducted in real time by the Drs. [name] and [name] together with Drs. [name] and [name], both of whom are MDs, the Project Director, Research Coordinators, and the IRBs at Mount Sinai, Asaf Harofeh and Sheba and reported to the Data Safety and Monitoring Board. They will determine the severity of the event, will assign attribution to the event, and will monitor the event until its resolution. All adverse events will be indicated on the source documentation for the study, and on the specific adverse event report form. The following information about adverse events will be collected: 1) the onset and resolution of the AE, 2) an assessment of the severity or intensity (use existing grading scales whenever possible), 3) an assessment of the relationship of the event to the study (definitely, probably, possibly or not related), and 4) action taken (e.g., none, referral to MD, start or adjust concomitant medication). All serious adverse events (SAEs) will be reported to the three sites' IRBs within 24 hours of the investigative team learning about them. The initial report will be conducted by phone, email or fax. This initial contact will later be followed by a written report to the IRB (using their SAE reporting form). All serious adverse events (SAEs) will be reported to the DSMB within 48 hours.

F. INCLUSION OF WOMEN AND MINORITIES- Since in Israel about half of those above the age of 65 who have type 2 diabetes are women, we anticipate a similar proportion of women in the RCT. A large proportion of the Israeli elderly are immigrants from approximately 60 countries and there is **no** exclusion criteria for any country of origin, ethnic group or religion.

G. INCLUSION OF CHILDREN- Children will not participate in this study since it investigates the elderly.

CLINICALTRIALS.GOV REQUIREMENT- This project includes a trial which requires registration in 26

ClinicalTrials.gov. The project will be registered with ClinicalTrials.gov.

1. Bureau USC. Interim Projections by Age, Sex, Race, and Hispanic Origin. 2004.

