Elderly with T2D have higher risk of developing dementia, MCI, and cognitive decline. T2D is a vascular disease culminating in tissue hypoxia, so cerebrovascular disease is the primary contributor to this increased risk. Impairment of cerebrovascular integrity in T2D may lead to reduced CBF on the vessel level, and reduced glucose metabolism on the neuronal level, which may be rectified with HBOT by cerebral vascular repair processes. We thus propose a randomized controlled trial (RCT) of the beneficial effects of HBOT on cognition and on ischemic injury (through assessment of CBF using MRI, and of glucose metabolism using FDG-PET). We focus on T2D elderly with MCI, who are enriched in cerebrovascular disease and are in the prodromal phase of the dementia process, an ideal opportunity for HBOT to protect and enhance cognition by reversing, preventing, or delaying neuropathologic processes that cause cognitive decline. We will test the extent to which 60 sessions of 90 minutes of 100% oxygen at 2 ATA—compared with a sham condition—improve cognitive performance in the short term (immediately after treatment) and a longer term (12 months after treatment). Subjects will be recruited through talks in the community, advertisements, and companies which have large lists of elderly interested in receiving emails about health related topics. In addition, we have a large-scale project in Israel (NIA R01AG034087), where 1200 T2D elderly are followed for cognitive decline providing an additional large recruitment source.

We hypothesize that HBOT compared to a sham condition (n=77 in each group) improves cognitive function and favorably alters cerebrovascular pathology (increasing CBF and glucose utilization) in T2D patients with MCI, focusing on the following outcomes:

Aim 1. Cognitive functioning: Aim 1a: *The primary outcome will be a composite measure of cognitive function balancing tests of both executive and memory function. Domain-specific measures of cognition (executive function and episodic memory) will be secondary outcomes.*

Aim 2. Ischemic Injury: CBF at the level of capillaries in gray matter measured by MRI arterial spin labeling, and in macrovessels, measured by a novel 4D Flow MRI technology developed by our group.

Aim 3. Neuronal function: [F18]FDG-PET measuring cerebral glucose utilization.

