D1h. A multidisciplinary team of integrated and productive investigators covering all the necessary expertise for successful implementation of this RCT: [name] (PI) is an expert in the neuropsychology of cognitive aging and dementia, with a main focus on the contribution of T2D; [name] (joint PI) is a neuropsychologist who is a national leader in clinical trials for MCI and dementia; [name] (PI Asaf Harofeh) is a world renowned expert of HBOT; [name] (PI: U Wisconsin site) is an expert in neuroimaging of dementia and focuses on metabolic disorders' effects on the brain; [name] (PI: Sheba site) is a geriatric psychiatrist, a young, rising physician-investigator; [name] is an internationally recognized expert in mechanisms underlying complications of T2D; [name] recent research focuses on the biological mechanisms of HBOT. [name] is a biostatistician with expertise in complex longitudinal analyses of clinical trials. [name] has published with all the PIs and has other joint grants with them. Thus, despite the distance, the team is well integrated, with expertise to ensure successful implementation of all components, analyses, and interpretation of results.

D2. Methods:

D2a. Participants- Elderly patients (n=250) with T2D and MCI (amnestic or non-amnestic) will be enrolled to examine potential HBOT therapeutic effects on the brain preceding dementia, when neuropathologic processes causing decline still have potential for prevention or delay. MMSE>24 and clinical dementia rating [CDR] = 0.5 will be required. An informant must be available for supplemental information throughout the trial.

Candidates will complete a cognitive assessment, physical and neurological examinations, and a clinical interview with an informant present. Cholinesterase inhibitors are an exclusion since their interaction with HBOT is not known. Subjects with an indication for HBOT (such as diabetic foot) will be excluded, to avoid randomization to the control arm. Israel is a country of immigration, so Hebrew fluency is required for valid neuropsychological testing⁸⁴. **Table 1** summarizes eligibility criteria. Subjects will be preferably from central Israel

Table 1: Eligibility criteria

Inclusion Criteria	Exclusion Criteria
1. Diagnosis of T2D	1. Brain disease that affects cognition (e.g. Parkinson's disease, schizophrenia).
2. Diagnosis of MCI	2. Stroke
3. \geq the age of 65	3. Epilepsy
4. Hebrew fluency	4. Chest pathology incompatible with HBOT

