5. An informant	5. Inner ear disease
	6. Claustrophobia
	7. Cholinesterase inhibitors
	8. Subjects with an indication for HBOT
	9. Individuals with previous HBOT treatments.
	10. Individuals with cancer and other medical illnesses requiring intensive therapy.
	11. Individuals with proliferative retinopathy.

since the HBOT treatment will be performed in Asaf Harofeh, located in central Israel. The treatment is very time consuming and far away participants may have a hard time complying to the treatment protocol.

D2b. Recruitment- Subjects will be recruited through talks in the community, advertisements, and companies which have large lists of elderly interested in receiving emails about health related topics. IDCD subjects diagnosed at follow up with MCI (21% at the 36-months follow up) will be offered participation in the proposed trial. Although the IDCD study participation was far less demanding than the proposed RCT, recruiting 1200 subjects within 2 years reinforces our confidence in recruiting 154 subjects for this RCT—including many already in the IDCD—in 3 1/2 years. Additional recruitment will be performed through clinics (e.g. diabetes and executive clinics).

Table 2- Summary of study procedures

	Screen	Baseline/ beginning of intervention	12 weeks /end of intervention	6 months	12 months
Informed consent	X				
History, cognitive assessment (for MCI classification), clinical evaluation	X				
Medication review	X	X	X	X	X
Physical exam	X		X		
Blood test		X	X		X
Follow up information		X	X	X	X
Adverse event monitoring*			X*		
Group assignment: review program and expectations at time of randomization		X			
Cognitive testing (ADAS COG13+executive functions tests)		X	X	X	X
Functional assessment (CDR)	X		X	X	X
ADL, IADL		X	X	X	X
Depression questionnaire	X		X	X	X
MRI ASL		X	X		X
FDG-PET		X	X		X
Blindness testing			X		
The intervention will begin within three weeks after the Baseline assessments and end at 12 weeks after 60 HBOT/Sham treatments. A physician is always present during the HBOT sessions, and a nurse is in the chamber throughout the whole treatment, so adverse events will be de facto closely monitored at each session up to the end of the intervention.					

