D2c. Procedures- **Table 2** presents study procedures for each subject. HBOT sessions will take place in Asaf Harofeh Medical Center; informed consent and all other assessments, including cognitive, functional, MRI, and FDG-PET will be performed at the Sheba Medical Center. Adverse event monitoring is done at every HBOT and sham session, by a nurse in the chamber throughout the session and a physician always present. Physical exams and blood collection for safety monitoring will occur before randomization, and at 12 weeks. Medication review will occur before randomization, before and after the intervention, and 6 and 12 months later, with cognitive testing at these times except before randomization. The T2D-related biomarkers (Blood test, MRI ASL and FDG-PET) will be assessed before and after the intervention, and 12 months later. After intervention, a questionnaire will examine whether blindness was maintained. At the end of the participant's 12 months' participation in the trial, the participant can choose to receive HBOT treatment for which the costs will be covered by the study team. At the end of the second HBOT treatment course, an additional neuropsychological assessment will be administered to the participants.

D2d. Randomization and Blinding of Intervention-Eligible candidates will be randomized with equal probability to the HBOT and sham interventions. When a cluster of at least 3 subjects from one of the interventions is filled, the intervention for that cluster will begin (77 subjects will be recruited for each treatment). Clusters will be a random effect in the analyses (see D6). Three study technicians who activate HBOT or sham protocol sessions will be the only unblinded staff who have the key for the subjects' group assignments. All subjects and other clinic staff will remain blinded to group assignment. Study nurses will monitor AEs during all sessions and a physician will be present during each session. Importantly, staff from Sheba, who assesses outcomes, will not be exposed to the subjects during their intervention and vice-versa.

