D3. Logistics and communication among the international investigators- [name] has collaborated for many years with all investigators and has numerous joint publications demonstrating her capability to effectively lead international studies with complex logistics. Drs. [name] and [name] will lead 2 biweekly conference calls. One, with the Sheba and the Asaf Harofeh teams, will discuss day-to-day aspects of the trial (recruitment, refusals and ways to overcome them, data entry and missing data, staffing and coordination, and adverse events). The other, with the senior investigators, Drs. [name], [name], [name], [name], and [name], will monitor overall progress toward the trial's goals. Both meetings will have minutes that will be sent to the meeting participants and action items will be reviewed in each meeting. Drs. [name] and [name] communicate very often on the neuroimaging aspects of other collaborative studies facilitating continuous communication on the proposed study. Images upload to the warehouse is done at the scan day and [name] has access to them (see D5).

Funds are allocated for Drs. [name] and [name] travel to Israel for close study supervision of progress, and for the annual AAIC conference where the senior investigators will meet face-to-face.

D4. Study Timelines- The first three months will be devoted to obtaining IRB approvals from all sites and training study physicians, neuropsychologists, and nurses for data collection. Screening and enrollment will occur from month 4 of the study and until the middle of year 4 (~47 subjects/year); data collection and cleaning will extend for another year. Analyses and preparation of the primary manuscript will be in the final 6 months.

D5. Data handling and transmission- The Mount Sinai Department of Psychiatry data management infrastructure is a web based data warehouse including all its cognition and AD projects. A region specifically designed for the proposed study includes MRI and PET scan data. The original study materials, including the MRI and PET scans, will be transmitted via a secure FTP. Data entry is through a web portal by a double entry system. The warehouse files have built-in range and logical checks to flag or prevent impossible values. Each study team member has identification to download data files via a secure web portal, so analyses do not affect warehoused data. Data transmission has been successful in the IDCD and our other international projects.

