Aim 1. Power is presented for detecting the difference in mean change (from baseline to 12 weeks) in overall cognition z-scores between the sham and HBOT treatment groups. Power calculations are based on two-sample t-tests and are conducted with a 2-sided 5% significance level (**Table 3**). A 2-sample t-test provides a more conservative power estimate than the proposed mixed model approach, which is expected to explain more variability and thus have more power to detect the same effect size with the same sample size.

The predicted mean change in the sham group from baseline to 12 weeks is -0.02 (based on the IDCD 12-week change in overall cognition). Assuming an SD of 0.50 in both the sham and HBOT groups, with a minimum sample size of 67 patients per arm, we have 80% power to detect an improvement in the HBOT group of 0.224, a “medium” effect size of 0.49. To account for an anticipated dropout rate of 13% (a reasonable estimate compared to the 5% dropout rate in our stroke study), we plan to enroll 77 patients per group for a total of 154 patients. Our HBOT trial years after mild traumatic brain injury⁷⁴ had an effect size of 0.47 for information speed processing which is clinically comparable to our primary outcome measure of overall cognition, and our HBOT trial on stroke patients⁷⁸ showed an effect size of 0.49 for the National Institutes of Health stroke scale, suggesting our detectable effect size of 0.49 is feasible.

Aim 2: As for Aim 1, power is presented for detecting the difference in the mean changes in CBF velocity and cerebral glucose utilization between the Sham and HBOT groups. Assuming a mean change in CBF velocity of -0.45 in the Sham group and an SD of 5.6 in both groups, with a minimum sample size of 67 patients per arm we have 80% power to detect an improvement in the HBOT group of 2.28, an effect size of 0.49. *To account for an anticipated dropout rate of 13%, we plan to enroll 77 patients per group for a total of 154 patients.* For cerebral glucose utilization, assuming a mean change in the sham group of -0.08 and an SD of 4.40 in both groups, with

Table 3: Two group t-test of equal means, equal n's)*			
	Outcome		
	Overall Cognition z-score	CBFV [†]	CGU [‡]
Sham Mean Change, D ₁	-0.020	-0.450	-0.08
HBOT Mean Change, D ₂	0.224	2.28	2.065
Difference in means, D ₁ -D ₂	-0.244	-2.73	-2.145
HBOT SD	0.50	5.60	4.40
Minimum N per group	67	67	67
Enrollment N per group**	77	77	77

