Involvement. The T2D subjects involved in this RCT will participate in neuropsychological assessments involving a clinical/diagnostic interview and paper and pencil tests. In addition, they will be interviewed in a risk factor inventory in which basic demographic, some medical information, and past behaviors (e.g. smoking, physical activity) will be assessed. In addition, subjects will go through an MRI examination and a PET scan. Subjects will be also asked about their activities of daily living and instrumental activities of daily living. Only subjects who have a diagnosis of T2D and a diagnosis of MCI will participate in the study. Subjects will be randomized to HBOT or sham. Both groups will be treated in the oxygen chamber for 60 sessions, 5 times/week, 90 minutes each session and will receive 100% oxygen. The HBOT group will have 2.0 ATA during the treatment while the sham group will receive 1.1 ATA during the first and last five minutes of the 90-minute sessions. All other conditions and assessments will be identical for the two groups. All assessments will be performed at baseline (before treatment), at 12 weeks (immediately after treatment) and at 12 months (to assess maintenance of HBOT effects in the long term). At 6 months, only the cognitive assessments will be assessed. Upon informed consent, subjects' long term diabetes characteristics (such as HbA1C, duration of disease, anti-diabetic medication status, and hypertension status) will be given by the subject who will provide the investigating team with the computerized medical chart from the HMO.

Characteristics. Eligibility criteria are summarized in **Table 1, section D2a** of the application. This study will consist of 154 elderly subjects (>65 years of age) who have T2D and a diagnosis of MCI (both amnestic and non-amnestic). Subjects must have at least one informant and must speak fluent Hebrew for the neuropsychological assessment. Subjects may not have a brain disease that might affect cognition such as schizophrenia or Parkinson's disease, they may not have epilepsy, inner ear disease, or claustrophobia. Subjects cannot be receiving cholinesterase inhibitors and cannot have an indication for HBOT, such as diabetic foot, since then they cannot be randomized to the sham group. There are no inclusion or exclusion criteria on the basis of sex, race, ethnicity, religion, or any other minority affiliations. Within the elderly, Israel is primarily a

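### D2a says 250 patients will be enrolled, but every other statement of size gives or implies 154 (77 per arm); the 250 is undefined and unreconciled, and only 154 follows from the power calculation.

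*Combined protocol and SAP*

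**What the plan says.** D2a (Participants) opens with the size and type of the study population: "Elderly patients (n=250) with T2D and MCI (amnestic or non-amnestic) will be enrolled". It gives no split by arm, no power basis and no accrual rate for that figure.

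The other statements of size agree with one another:

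- Hypothesis statement before Aim 1: "We hypothesize that HBOT compared to a sham condition (n=77 in each group".
- D2b (Recruitment): previous recruitment experience "reinforces our confidence in recruiting 154 subjects for this RCT", over three and a half years.
- D2d (Randomization and Blinding): "77 subjects will be recruited for each treatment".
- D4 (Study Timelines): screening and enrolment run from month 4 "until the middle of year 4 (~47 subjects/year".
- D7 (Power Analysis): "we plan to enroll 77 patients per group for a total of 154 patients". Table 3 also shows 77 enrolled per group.
- Section E, Characteristics: "This study will consist of 154 elderly subjects (>65 years of age) who have T2D and a diagnosis of MCI".

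**The concern.** D2a uses the same verb for 250 that D7 uses for 154, and applies it to patients who already have both diabetes and MCI. On its face it is an enrolment target, and it is 96 above the other one (96/154 = 62% more).

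The sample size determines when recruitment ends, what the ethics committees approve and what the power statement covers. A reader who takes D2a at its word cannot match it to Table 3, to the per-arm figure in the randomisation section or to the timeline. The text reviewed describes no interim analysis or sample-size re-estimation that would move the target from one figure to the other.

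**Working it through.** **Inputs.** From D7 and Table 3: two-sample t-test, two-sided 5%, 80% power, sham change -0.020, HBOT change 0.224, SD 0.50 in both arms, 13% dropout. From D2d: 1:1 allocation. From D4: about 47 a year, month 4 to the middle of year 4, which is 42 - 3 = 39 months, or 3.25 years. From D2b: 3.5 years. From D2a: 250.

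**Step 1: reproduce the plan's figure.**
- Difference: 0.224 - (-0.020) = 0.244. Standardised: d = 0.244/0.50 = 0.488.
- The noncentral t calculation gives n = 66.9, so 67 per arm. Power at 67 per arm is 80.1%.
- The imaging outcomes give nearly the same d: 2.73/5.60 = 0.4875 for CBF and 2.145/4.40 = 0.4875 for glucose utilisation. Power at 67 per arm is 79.98% for each.
- Dropout: 67/(1 - 0.13) = 77.01, taken as 77. Strict rounding up would give 78, which is immaterial.
- Total: 2 × 77 = 154. The plan's figure is reproduced.

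**Step 2: check the timeline against each figure.**
- 47 × 3.25 = 152.75, about 153, which fits 154.
- At 47 a year, 250 would take 250/47 = 5.3 years.
- To fit the window, 250 would need 250/3.25 = 77 a year, or 250/3.5 = 71 a year on D2b's duration.

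**Step 3: try to derive 250 from the plan's inputs.**
- For 250 enrolled to leave the 2 × 67 = 134 evaluable, attrition would be 1 - 134/250 = 46%, against the stated 13%.
- So 250 is not 154 under a different dropout allowance that the plan mentions.

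**Step 4: what would follow if all 250 were randomised.** This is conditional, since no section says so.

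| | 154 randomised | 250 randomised |
|---|---|---|
| Per arm | 77 | 125 |
| Evaluable per arm after 13% dropout | 67 | 125 × 0.87 = 108.75, taken as 108 |
| Power at d = 0.488 | 80.1% | 94.6% |
| Detectable d at 80% power | 0.488 | 0.383 |
| Detectable difference (SD 0.50) | 0.244 | 0.191 |
| Accrual per year (3.5 to 3.25 years) | 44 to 47 | 71 to 77 |

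**The case against.** The strongest reply is that 250 may count people consented or screened. Table 2 places informed consent at the screening visit, together with the assessment used for MCI classification, and group assignment comes later, at baseline. D2a itself goes on to describe candidates being assessed. A consented pool larger than the randomised set is therefore built into the design, and 250 consented with 154 randomised (154/250 = 61.6%) is possible. This stands as a possibility. It is not established: D2a attaches 250 to patients who already have the diagnoses, uses the verb that D7 uses for 154, and no section reviewed gives a screen-failure rate or links the two numbers. Part of the preliminary-studies section (D1) was not in the text reviewed. If the reply is right, one word covers two populations and D2a still needs a clarifying line.

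A second reply is that the target is not really in doubt, because 77 per arm appears consistently, including in the section that governs allocation. That also has force. A reader might infer that the trial has two competing designs with no defined end to recruitment. The documents do not support that: they hold one derived, reproducible size and one isolated figure with nothing behind it.

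A third reply is that a larger trial would only have more power. That is correct for the primary test if all 250 were randomised, so the validity of that test is not at issue.

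**Conclusion.** The inconsistency is real and stands in the current body text. The 250 in D2a conflicts with the 154 stated or implied everywhere else, and 154 is the only size that the power calculation supports. The calculation itself is sound, and Table 3 is correct for the size it covers.

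Three stronger conclusions should not be drawn. The two numbers are not shown to be irreconcilable, because a consented or screened count of 250 would be compatible with 154 randomised. The documents do not show that 250 is a mistake, a screening number or a revision not carried through. Nor do they show that 96 extra people will be treated. That exposure, 60 scheduled chamber sessions and three FDG-PET scans each, arises only if 250 means randomised. The 60 sessions are the randomised course and not a ceiling, since D2c offers optional HBOT after the 12 months.

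The power and accrual figures for 250 carry the same condition, and also assume 1:1 allocation and the plan's own SD and 13% dropout.

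**What to change.** First, the sponsor should confirm what 250 counts. D2a should then state the randomisation target as 154 (77 per arm). If 250 is a number consented or screened, D2a should give it separately and label it so. In that case, or if 250 is simply an error, the cost is one line.

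Only if 250 is the true randomisation target should the other sections change: the hypothesis statement, D2b, D2d, D4, D7 with Table 3 and the human-subjects section would all need restating for 125 per arm, with the power, detectable effect and accrual rate given above. That means edits to several sections and a stated justification for the larger size, which the plan does not now contain.
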